9.3. Variables

Baseline variables (Table 2) will be measured during the baseline period (365 days prior to the index date). Treatment patterns, adherence and persistence, and clinical variables (Table 3) will be measured during the follow-up period.

Table 2. Baseline demographic and clinical characteristic variables

Variable	Operational definition
Age	Age will be defined as of the index date and retained in the dataset as a continuous variable and a categorical variable (e.g., ≤ 59 , 60-69, 70-79, ≥ 80 years old).
Race/ethnicity	Proportion of patients that were non-Hispanic White, Black, Hispanic, other or unknown will be summarized.
Geographic regions	Proportion of patients that lived in Northeast, Midwest, South and West areas will be summarized.
Index year	A categorical variable for the index calendar year will be summarized.
Site of metastasis	Proportion of patients that had a metastatic diagnosis at the following sites: bone only, bone and node only, node

PFIZER CONFIDENTIAL

Variable	Operational definition
	only, viscera and other, will be summarized among patients with metastatic PC. All data available prior to the index date will be used.
Treatment history	
Proportion of patients who had each of the following treatments in the baseline period will be evaluated:
 
• Prostatectomy• Chronic oral corticosteroid use• Pain medication (opioids)• ADT treatment (leuprolide, degarelix, goserelin, histrelin, triptorelin)• Androgen receptor pathway inhibitor (ARPI; abiraterone, apalutamide, darolutamide, enzalutamide)• Non-steroidal anti-androgen (NSAA; bicalutamide, nilutamide, flutamide)• Chemotherapy (docetaxel, cabazitaxel, carboplatin, oxaliplatin, cisplatin, mitoxantrone)• Immunotherapy (sipuleucel-T, pembrolizumab)• Radium 223• Systemic ketoconazole• Olaparib• Rucaparib• Talazoparib• Niraparib• Lutetium Lu 177 vipivotide tetraxetan• Radiotherapy 
Treatments considered as a part of index treatment regimen will not be flagged as baseline treatments if received within 30 days prior to index date.

Time from first observed PC diagnosis date to the index date	Time from the first observed PC date in the data to the index date will be evaluated. All data available prior to the index date will be used.
NCI Charlson Comorbidity Index (CCI) score	The NCI version of the CCI score will be created during the baseline period.

Variable	Operational definition

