Index treatment	
Index treatment regimens include:
 
 • Relugolix monotherapy • Relugolix + NSAA only (at least 90 days of NSAA use) • Relugolix + ARPI +/- NSAA (no chemotherapy) • Relugolix + ARPI + chemotherapy • Relugolix + chemotherapy +/- NSAA (no ARPI) • Relugolix + other (no ARPI, no chemotherapy) 
Index treatment regimen will be defined based on treatments received within 30 days before the index date and within 90 days after the index date.
 
Specific treatments included in each treatment category (i.e., ADT, NSAA, ARPI, chemotherapy, immunotherapy) are described in “Treatment history” in Table 2. Other treatments include immunotherapy, radium 223, olaparib, rucaparib, talazoparib, niraparib and lutetium Lu 177 vipivotide tetraxetan.
 
Number of patients who received any radiotherapy during the index treatment will be summarized.

Variable	Operational definition
Treatment patterns of relugolix	
Treatment patterns of relugolix include:
 
• Continued relugolix as in the index treatment (regardless of discontinuation of concomitant medications)• Continued relugolix with a new add-on systemic PC treatment (excluding ADT)• Discontinued relugolix and switched to another ADT treatment• Discontinued relugolix without switching to another ADT treatment 
Add-on systemic PC treatments include:
 
• ARPI• NSAA• Chemotherapy• Immunotherapy• Radium 223• Ketoconazole• Olaparib• Rucaparib• Talazoparib• Niraparib• Lutetium Lu 177 vipivotide tetraxetan 
Add-on therapy will be evaluated from 90 days after the index period to the end of the follow-up period.

Time to treatment changes	The time to treatment changes of interest include: 
• Time to discontinuation of relugolix• Time to switching to a different ADT treatment• Time to add a new systemic PC treatment to relugolix
Treatment adherence	Adherence to relugolix post the index date will be described using both MPR and PDC: 
• MPR: Sum of the days of supply divided by the number of days between the first fill and the end of the last refill (i.e., including the days of supply from the last refill)• PDC: Sum of the non-overlapping (i.e., not double counting of overlaps) days of supply covered

Variable	Operational definition

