9.5. Study size

As no priori hypotheses are specified, sample size calculations are not applicable. The number of patients eligible for the study will be determined in accordance with the sample selection conducted per the criteria described in Section 9.2.

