9.7.2.3. Time to treatment changes

Kaplan-Meier analysis will be conducted to describe the following time-to-event outcomes for the treatment patterns as listed in [Table 3](#):

PFIZER CONFIDENTIAL

- Time to discontinuation of relugolix
- Time to switching to a different ADT treatment
- Time to add a new systemic PC treatment to relugolix

The number and proportion of patients with the corresponding event will be plotted over time and the number at risk table over time will be presented. The median time to event will be calculated.

9.7.3. Data analysis for Objective 3: To estimate adherence and persistence with relugolix among patients with PC who initiated relugolix

Adherence to relugolix as defined in [Table 3](#) will be described. MPR will be summarized over the entire exposure to relugolix during the follow-up period. PDC will be summarized within the 6, 12, and 18 months (tentatively, pending on the final length of follow-up) since the index date. Means, standard deviations, medians, and interquartile range will be estimated for adherence as a continuous variable. Counts and percentages will be estimated for adherence as a binary variable. Patients will be required to have complete follow-up data during the time to be included in each adherence calculation.

Persistence to relugolix as defined in [Table 3](#) will be described using Kaplan-Meier analysis since the index date. The number and proportion of patients persistent to relugolix will be plotted over time and the number at risk table over time will be presented.

9.7.4. Data analysis for Objective 4: To assess testosterone suppression and PSA responses among ADT naïve patients with PC who initiated relugolix

If sample size is sufficient, the count and percentage of patients with testosterone responses as defined in [Table 3](#) will be calculated among ADT naïve patients with at least one testosterone measure during the follow-up period. Similarly, if sample size is sufficient, the count and percentage of patients with PSA responses as defined in [Table 3](#) will be calculated among ADT naïve patients with at least one baseline and one follow-up period PSA measure.

9.7.5. Data analysis for Objective 5: To describe and compare demographics and clinical characteristics between Black and non-Hispanic White patients with PC who initiated relugolix

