ANNEX 2. ADDITIONAL INFORMATION

Appendix Table 1. Codes for PC treatments

	GPI	HCPCS/CPT	ICD
ADT			
		CPT 54520, 54522, 54530, 54535, 54690	ICD-10-CM Z90.79
Orchiectomy			ICD-10-PCS 0V590ZZ, 0V593ZZ, 0V594ZZ, 0V5B0ZZ, 0V5B3ZZ, 0V5B4ZZ, 0V5C0ZZ, 0V5C3ZZ, 0V5C4ZZ, 0VT90ZZ, 0VT94ZZ, 0VTB0ZZ, 0VTB4ZZ, 0VTC0ZZ, 0VTC4ZZ
LHRH agonists/antagonists			
Degarelix	2140552510	J9155	
Goserelin	21405005	J9202	
Histrelin	2140500710	J1675, J9225, J9226, S0133	
Leuprorelin	21405010	J1950, J9217, J9218, J9219, Q0057	
Relugolix	21405570000320, 24993503800320		
Triptorelin	21405050	J3315	
ARPI			
Apalutamide	2140241000		
Abiraterone	2140601020		
Darolutamide	2140242500		
Enzalutamide	2140243000		
NSAA			
Bicalutamide	2140242000		
Flutamide	2140244000		
Nilutamide	2140246000		
Chemotherapy		HCPCS	ICD
Cabazitaxel	2150000300	C9276, J9043	
Docetaxel	2150000500	J9170, J9171	
Carboplatin	2110001500	J8530, J9070, J9080, J9090, J9091, J9092, J9093, J9094, J9095, J9096, J9097	

PFIZER CONFIDENTIAL

CT24-WI-GL02-RF02 5.0 Non-Interventional Study Protocol Template For Secondary Data Collection Study 01-Aug-2023

Page 35 of 41

Cisplatin	2110002000	J9045	
Oxaliplatin	2110002800	J9263	
Mitoxantrone	2120005500	J9293	
Immunotherapy		HCPCS	ICD
Sipuleucel-T	2165107000	Q2043, C9273	
Pembrolizumab	21357953002	J9271, C9027	
Others		HCPCS	ICD
Radium-223	2160005500	A9606	
Ketoconazole	1140404000, 9630106400, 9015404500		
Olaparib	21535560		
Lutetium Lu 177 vipivotide tetraxetan	21600045802020	A9607	
Niraparib	21535550200, 21409902120		
Talazoparib	215355804001		
Niraparib	21535550200, 21409902120		
Rucaparib	21535570		

Abbreviations: ADT: androgen deprivation therapy; ARPI: androgen receptor pathway inhibitor; CTP: Current Procedural Terminology; GPI: Generic Product Identifier; HCPCS: Healthcare Common Procedure Coding System; ICD: International Classification of Diseases; ICD-10-CM: International Classification of Diseases, 10th Revision, Clinical Modification; ICD-10-PCS: International Classification of Diseases, 10th Revision, Procedures; LHRH: luteinizing hormone-releasing hormone; NSAA: non-steroidal anti-androgen

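### Ketoconazole counts as an add-on treatment but fits no index regimen, and its code list does not apply the systemic restriction set in Table 2

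*Combined protocol and SAP*

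**What the plan says.** Four places define how ketoconazole is handled.

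- **Section 9.3, Table 2, treatment history.** The baseline item is "Systemic ketoconazole". A treatment that forms part of the index regimen is not flagged as baseline treatment if it was received in the 30 days before index.
- **Section 9.3, Table 3, index treatment.** Six regimens are built from relugolix, NSAA, ARPI, chemotherapy and a group of other treatments, using the window from 30 days before to 90 days after index. The sentence that begins "Other treatments include immunotherapy, radium 223, olaparib" goes on to rucaparib, talazoparib, niraparib and lutetium, and stops there. Ketoconazole is not named.
- **Section 9.3, Table 3, treatment patterns.** The list headed "Add-on systemic PC treatments include" does name ketoconazole, without a route qualifier. Add-on therapy is evaluated only from 90 days onward. The list feeds the add-on pattern in the Sankey diagram and the endpoint "Time to add a new systemic PC treatment to relugolix" (Section 9.7.2.3), which Section 9.7.6 compares by race with Cox models.
- **Annex 2, Appendix Table 1.** A single row labelled ketoconazole carries the GPI codes "1140404000, 9630106400, 9015404500". No route or dosage form is given.

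**The concern.** There are two faults, and each stands without the other.

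First, the index list and the add-on list should be built from the same agents. If a drug can be an add-on but can never be part of the index regimen, a patient already on it is described wrongly at index and may then appear to change treatment when he has not. That affects the index regimen distribution, the Sankey add-on pattern and the time-to-add-on curve.

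Second, a programmer working from Appendix Table 1 would pull every ketoconazole product under three codes. The systemic restriction appears in Table 2 and in the heading of the Table 3 list, but no step applies it to the codes. If any of the codes covers a non-systemic product, a fill of that product would be recorded as prior or new systemic prostate cancer treatment, and nothing in the output would show it.

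**Working it through.** The plan gives no figure to reproduce, so the check compares the lists and the codes.

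**Step 1. Match each add-on entry to an index category (both in Table 3).**

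| Add-on entry | Index category |
|---|---|
| ARPI | ARPI regimens |
| NSAA | NSAA regimen (with a 90-day minimum), or alongside ARPI or chemotherapy |
| Chemotherapy | Chemotherapy regimens |
| Immunotherapy, radium 223, olaparib, rucaparib, talazoparib, niraparib, lutetium Lu 177 | Relugolix + other |
| Ketoconazole | None |

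Of the 11 add-on entries, 10 have an index category. Ketoconazole is the only one without.

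**Step 2. Apply the rules to two hypothetical men.** Day 90 is counted here from the index date. Table 3 refers to an index period that it does not define; a later start would move the dates but not the logic.

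- Man A starts olaparib on day 40 and refills on day 100. His index regimen is relugolix + other. The day-100 fill belongs to that regimen and is not new.
- Man B starts ketoconazole on day 40 and refills on day 100. No index category fits except relugolix monotherapy. The day-100 fill falls in the add-on period and is of a drug outside his index regimen.

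Table 3 does not define new. If it means not part of the index regimen, man B has an add-on event at day 100, dated 60 days after the true start (100 − 40 = 60). If it means never received before, he has no event. Under both readings he is misclassified as monotherapy.

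**Step 3. Effect on the baseline item.** Because ketoconazole is never part of an index regimen, the Table 2 rule for the 30 days before index cannot apply to it. A man with a fill in those 30 days is flagged as having prior ketoconazole and is also classed as monotherapy. The same fill pattern for an agent in the other-treatments group would be assigned to the index regimen instead.

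**Step 4. Tabulate the leading two digits of the GPI codes in Appendix Table 1.** Counting the repeated niraparib row once, there are 32 distinct codes for 28 drugs.

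| Leading pair | Codes | Drugs |
|---|---|---|
| 21 | 28 | every drug except ketoconazole |
| 24 | 1 | relugolix (second code) |
| 11, 96, 90 | 3 | ketoconazole |

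Check: 28 + 1 + 3 = 32. Ketoconazole is the only drug with three leading pairs and the only one with no code under 21. Elsewhere the plan selects whole drug groups by short leading strings: Appendix Table 3 uses 65 for opioids and 22, 8910 and 8915 for corticosteroids. It is therefore reasonable to infer that the three ketoconazole codes belong to three product groups. The documents contain no GPI dictionary, so they do not show the route of any of the three.

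**Step 5. Which outputs are touched.** Affected: the ketoconazole line of baseline treatment history (Objectives 1 and 5), the index regimen distribution, the Sankey add-on pattern and time to add-on (Objective 2), and the comparison of time to add-on by race (Objective 6). Not directly affected: time to discontinuation, time to switching, persistence, MPR and PDC. These depend on relugolix supply, a switch to another ADT, or death, and ketoconazole is not in the plan's ADT list.

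**The case against.** The strongest reply to the first fault is that an add-on must be new, and a man already taking ketoconazole at index is not starting anything new. That is a fair reading, and under it the false add-on event disappears. But the plan does not define the word, and the only regimen against which newness could be judged omits ketoconazole. The monotherapy misclassification remains in any case.

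The reply to the second fault is that the restriction is in the variable definitions and that the appendix is an ingredient-level list to be narrowed by them. Corticosteroids follow the same layout: Table 2 asks for chronic oral use, while Appendix Table 3 lists broad prefixes. This is plausible, and it limits the criticism to a narrowing step that is not written down. It does not supply that step, and Table 3 and Appendix Table 1 drop the systemic label from the drug itself.

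A reader might go further and infer that the codes beginning 90 and 96 are topical or otherwise non-systemic products that should simply be deleted. The documents do not support that. Differing leading digits do not prove a different route: relugolix is listed under "21405570000320, 24993503800320", two leading pairs for one drug. Deleting an unverified code could also lose genuine systemic use.

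**Conclusion.** Wrong as written, on both counts. The mismatch between the index and add-on lists follows from Table 3 alone and does not depend on what the GPI codes mean. The systemic restriction is stated but not put into operation; whether any non-systemic product is actually captured is unknown.

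The size cannot be computed, because the documents give neither ketoconazole use by product nor an add-on rate. I expect it to be small: ketoconazole is one of 11 add-on entries and one of 16 baseline treatment-history items. That is a judgement, not a result. A reader might be tempted to put a percentage on false add-on events, but any such figure would rest wholly on assumed rates. A reader might also infer a bias in the comparison of Black and non-Hispanic White patients. Nothing in the documents suggests that ketoconazole use, systemic or not, differs by race, so no direction can be claimed.

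The primary objective is touched through one descriptive baseline line. The other affected analyses are exploratory, apart from which Section 9.5 notes: "As no priori hypotheses are specified, sample size calculations are not applicable". This is a definition to correct before programming, not a threat to the study's main description.

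**What to change.** 1. In Table 3, add systemic ketoconazole to the index list of other treatments, so that the index and add-on lists contain the same agents.
2. In Table 3, state that an add-on counts as new only if the agent was not received in the index window (30 days before to 90 days after index).
3. Check the three ketoconazole codes against the GPI dictionary. Apply a systemic filter by route or dosage form, and drop any code found not to be systemic. If the data hold no usable route field, list the eligible products at a longer code length, as is done for relugolix with 14 digits, against 10 for ketoconazole.
4. Use the label systemic ketoconazole in Tables 2 and 3 and in Appendix Table 1.

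The cost is a few words, one dictionary check and one filter, with no new data. There are two side effects. Ketoconazole fills in the 30 days before index would move from baseline history to the index regimen, in line with the rule for other agents. The definition of new would also apply to a man with under 90 days of NSAA in the index window who restarts it later: he would not count as an add-on, and the team should confirm that this is intended.

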Appendix Table 2. Diagnosis codes for comorbidities

Conditions and comorbidities	ICD-10-CM
NCI comorbidity index¹	
Cerebrovascular disease	G45, G46, H34.0, I60–I69
Chronic pulmonary disease	I27.8, I27.9, J40–J47, J60– J67, J68.4, J70.1, J70.3
Congestive heart failure	I09.9, I11.0, I13.0, I13.2, I25.5, I42.0, I42.5–I42.9, I43, I50, P29.0
Dementia	F00–F03, F05.1, G30, G31.1
Diabetes with chronic complication	E10.2–E10.5, E10.7, E11.2– E11.5, E11.7, E12.2–E12.5, E12.7, E13.2– E13.5, E13.7, E14.2–E14.5, E14.7
Diabetes without chronic complication	E10.0, E10.1, E10.6, E10.8, E10.9, E11.0, E11.1, E11.6, E11.8, E11.9, E12.0, E12.1, E12.6, E12.8, E12.9, E13.0, E13.1, E13.6, E13.8, E13.9, E14.0, E14.1,

PFIZER CONFIDENTIAL

CT24-WI-GL02-RF02 5.0 Non-Interventional Study Protocol Template For Secondary Data Collection Study 01-Aug-2023
Page 37 of 41

	E14.6, E14.8, E14.9
Hemiplegia or paraplegia	G04.1, G11.4, G80.1, G80.2, G81, G82, G83.0–G83.4, G83.9
Mild liver disease	B18, K70.0– K70.3, K70.9, K71.3–K71.5, K71.7, K73, K74, K76.0, K76.2–K76.4, K76.8, K76.9, Z94.4
Moderate or severe liver disease	I85.0, I85.9, I86.4, I98.2, K70.4, K71.1, K72.1, K72.9, K76.5, K76.6, K76.7
Peripheral vascular disease	I70, I71, I73.1, I73.8, I73.9, I77.1, I79.0, I79.2, K55.1, K55.8, K55.9, Z95.8, Z95.9
Renal disease	I12.0, I13.1, N03.2–N03.7, N05.2–N05.7, N18, N19, N25.0, Z49.0– Z49.2, Z94.0, Z99.2
Individual conditions	

PFIZER CONFIDENTIAL

CT24-WI-GL02-RF02 5.0 Non-Interventional Study Protocol Template For Secondary Data Collection Study 01-Aug-2023

Page 38 of 41

Hypertension	H35.039, I10–I13, I15–I16, I67.4
Hyperlipidemia	E78.00, E78.01, E78.1, E78.2, E78.3, E78.41, E78.49, E78.5
Type II diabetes	E10.0, E10.1, E10.6, E10.8, E10.9, E11.0, E11.1, E11.6, E11.8, E11.9, E12.0, E12.1, E12.6, E12.8, E12.9, E13.0, E13.1, E13.6, E13.8, E13.9, E14.0, E14.1, E14.6, E14.8, E14.9
Urinary tract infection	
Chronic obstructive pulmonary disease	J40, J41, J42, J43, J47, J44.9
Arrhythmia	I47.0, I47.2, I49.0, I46, I49.3, I49.49, I47.9, I49.40, I49.5, I49.8, I49.9
Congestive heart failure	I09.9, I11.0, I13.0, I13.2, I25.5, I42.0, I42.5–I42.9, I43, I50, P29.0
Myocardial infarction	I21, I22, I25.2

Stroke	I60, I61, I62, I64, I65, I67, H34.1, H34.23, H34.21, H34.0
Angina pectoris	I20
Inflammatory bowel disease	K50, K51
Acute coronary syndrome	I24, I21
Sexual dysfunction	F52.21, N52
Depression	F20.4, F31.3- F31.5, F32, F33, F34.1, F41.2, F43.2
Anxiety	F06.4, F41, F43.22, F43.23, F93.0
Cognitive impairment	G30, G31.0, F01, F05, R41.0, R41.82, F10.1, F10.2, G31.2, G31.83, F02, F03, G31.1, G31.84, F06.7, R41.3, R41.81, R41.840
Hot flashes	R23.2
Primary cancers	C00-C21, C22.1-C22.7, C23-C76, C80.1, C80.2, C81-C96, C7A

Abbreviations: ICD-9-CM: International Classification of Diseases, 9th Revision, Clinical Modification; ICD-10-CM: International Classification of Diseases, 10th Revision, Clinical Modification; NCI: National Cancer Institute

[1] Source: Quan, Hude, et al. Coding algorithms for defining comorbidities in ICD-9-CM and ICD-10 administrative data. Medical care (2005): 1130-1139. Adapted using codes found in NCI Comorbidity Index Overview: <https://healthcaredelivery.cancer.gov/seermedicare/considerations/comorbidity.html>

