Comorbidities	A binary variable (yes/no) will be created for patients with a diagnosis of each of the following comorbidities during the baseline period: 
• Hypertension• Hyperlipidemia• Diabetes• Urinary tract infection• Chronic obstructive pulmonary disease• Arrhythmia• Congestive heart failure• Myocardial infarction• Stroke• Angina pectoris• Inflammatory bowel disease• Acute coronary syndrome• Sexual dysfunction• Depression• Anxiety• Hot flashes• Cognitive impairment• Major adverse cardiovascula event (defined by any evidence of cardiomyopathy, heart failure, ischemic heart disease, myocardial infarction, pulmonary embolism, or stroke)
PSA	Baseline PSA value (among available) based on the PSA value closest to the index date during the 90-day window (or 180-day, to be finalized based on the number of patients with non-missing PSA value in these time frames) on or prior to the index date will be evaluated.
Testosterone	Baseline testosterone value (among available) based on testosterone value closest to the index date during the 90-day window (or 180-day; will be consistent with the time window for baseline PSA) on or prior to the index date will be evaluated.
Metastatic vs. non-metastatic PC	A binary variable for patients with metastatic vs. non-metastatic PC will be created. Metastatic PC will be

Variable	Operational definition
	defined as having evidence of metastasis during the baseline period or within 90 days since the index date.
ADT naïve vs. ADT experienced	A binary variable for patients who were ADT naïve vs. ADT experienced will be created. ADT naïve will be defined as having no records of any systemic ADT treatment ever based on all available data prior to the index date (i.e., including baseline period data and any available data prior to the baseline period). Systemic ADT treatment includes LHRH agonists and GnRH antagonists (i.e., degarelix, relugolix, goserelin, histrelin, leuprolide, triptorelin)

Table 3. Treatment patterns, adherence, persistence, and clinical variables during the follow-up period

Variable	Operational definition

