9.7. Data analysis

9.7.1. Data analysis for Objective 1: To describe demographics and clinical characteristics of patients with PC who initiated relugolix

Descriptive analysis will be conducted for baseline demographics and clinical characteristics. Means, standard deviations, medians, and interquartile range will be estimated for continuous variables. Counts and percentages will be estimated for categorical variables. If the sample sizes allow, standardized mean difference (SMD) will be calculated to compare the patient baseline characteristics between metastatic vs. non-metastatic PC cohorts. For each variable, the SMD will be calculated as the difference in mean between two cohorts divided by the standard

deviation of the two cohorts pooled together. The absolute value of a SMD $> 10\%$ will be considered as an indicator for significant imbalance.

9.7.2. Data analysis for Objective 2: To assess treatment patterns among patients with PC who initiated relugolix

[figure not shown]

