The same descriptive analysis described in [Section 9.7.1](#) will be conducted in Black and non-Hispanic White patients separately. If the sample sizes allow, SMD will be calculated to compare the patient baseline characteristics between Black vs. non-Hispanic White cohorts. Additionally, p-values from appropriate statistical tests (e.g., t-tests or rank-sum tests for continuous variables and chi-square tests for categorical variables) comparing Black vs. non-Hispanic White cohorts will be reported.

9.7.6. Data analysis for Objective 6: To describe and compare time to treatment changes between Black and non-Hispanic White patients with PC who initiated relugolix

The same descriptive analyses described in Section 9.7.2.3 will be conducted in Black and non-Hispanic White patients separately. Unadjusted and adjusted comparisons between the two race groups will be conducted. Cox proportional hazards (PH) regressions will be used to compare the time to treatment changes between the two race groups. Patient characteristics to be included in the adjusted models will be selected based on findings in Section 9.7.5 and clinical input.

9.7.7. Data analysis for Objective 7: To estimate and compare adherence and persistence with relugolix between Black and non-Hispanic White patients with PC who initiated relugolix

The same descriptive analyses described in Section 9.7.3 will be conducted in Black and non-Hispanic White patients separately. Unadjusted and adjusted comparisons between the two race groups will be conducted. Generalized linear models will be used to compare adherence to relugolix between the two race groups. Cox PH regressions will be used to compare persistence between the two race groups. Patient characteristics to be included in the adjusted models will be selected based on findings in Section 9.7.5 and clinical input.

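### The code list behind the baseline diabetes flag covers neither all diabetes nor type II diabetes

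*Combined protocol and SAP*

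**What the plan says.** Table 2 in Section 9.3 introduces the comorbidity flags with "A binary variable (yes/no) will be created for patients with a diagnosis of each of the following comorbidities during the baseline period". Diabetes is one of the 18 conditions listed, and nothing there restricts it by type or by complication.

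Appendix Table 2 in Annex 2 supplies the codes, and diabetes appears in three of its rows:

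- **NCI index, diabetes with chronic complication.** The list begins "E10.2–E10.5, E10.7, E11.2– E11.5, E11.7" and continues in the same pattern through E14.
- **NCI index, diabetes without chronic complication.** It gives the .0, .1, .6, .8 and .9 codes of E10 through E14.
- **Individual conditions, headed type II diabetes.** It gives the .0, .1, .6, .8 and .9 codes of E10 through E14, ending "E13.0, E13.1, E13.6, E13.8, E13.9, E14.0, E14.1, E14.6, E14.8, E14.9".

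The third row is the only one that can serve the Section 9.3 flag. The two NCI rows feed the Charlson score, for which Section 9.3 says "The NCI version of the CCI score will be created during the baseline period".

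**The concern.** The variable name, the row heading and the code list describe three different things: diabetes, type II diabetes, and diabetes without chronic complication of any type. A programmer who follows the appendix will code the third. A patient whose only diabetes codes in the 365-day baseline are chronic-complication codes is then recorded as having no diabetes.

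Describing baseline clinical characteristics is the primary objective, so the flag is a primary output. It is also used in later analyses:

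- **Section 9.7.1:** if sample sizes allow, "standardized mean difference (SMD) will be calculated to compare the patient baseline characteristics between metastatic vs. non-metastatic PC cohorts", with an absolute value above 10% read as imbalance.
- **Section 9.7.5 (Objective 5):** p-values, and SMDs if sample sizes allow, compare Black and non-Hispanic White patients.
- **Sections 9.7.6 and 9.7.7 (Objectives 6 and 7):** "Patient characteristics to be included in the adjusted models will be selected based on findings in Section 9.7.5 and clinical input". The flag reaches these models only if it is selected.

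**Working it through.** The plan states no figure to reproduce. The check compares the three code lists in Appendix Table 2.

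**Inputs, written out in full**

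- A, type II diabetes (individual conditions): 5 families (E10 to E14) × 5 suffixes (.0, .1, .6, .8, .9) = 25 codes.
- B, without chronic complication (NCI): 5 families × the same 5 suffixes = 25 codes.
- C, with chronic complication (NCI): 5 families × 5 suffixes (.2, .3, .4, .5, .7) = 25 codes.

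**Comparison**

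| Check | Result |
|---|---|
| A against B | identical, in the same order |
| A and C in common | 0 codes |
| B and C together | 25 + 25 = 50 codes, every E10 to E14 code from .0 to .9, no gap |
| Share of the printed diabetes codes in A | 25 of 50 |
| E11 codes in A | 5 of 10 (.0, .1, .6, .8, .9) |
| E11 codes absent from A | 5 (.2, .3, .4, .5, .7) |
| Codes in A outside E11 | 25 − 5 = 20 |

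**Reading as all diabetes.** A leaves out every code that the same table classes as diabetes with chronic complication.

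**Reading as type II.** A spans five families and drops the complication codes of each, so it fails whichever family is type II. The E11 counts assume that E11 is that family, which is general coding knowledge and is not stated in the documents.

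**Effect on prevalence.** Suppose all diabetes is the target. Let p be the prevalence under the full 50-code list and s the share of those patients who have only C codes at baseline. The flag then reports p × (1 − s), a relative understatement of s. The documents give neither p nor s. If type II is the target, the row both omits and adds codes, so the direction is unknown.

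**Effect on a group comparison, on assumed figures only.** Take p = 30% in both race groups, so the true SMD is 0, and s = 20% in one group. The reported prevalence there is 0.30 × 0.80 = 24%. The SMD below is the difference divided by the square root of the mean of the two variances.

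| s in the other group | Reported there | SMD |
|---|---|---|
| 20% | 0.30 × 0.80 = 24% | 0 |
| 30% | 0.30 × 0.70 = 21% | 0.03 / √[(0.24 × 0.76 + 0.21 × 0.79) / 2] ≈ 0.07 |
| 40% | 0.30 × 0.60 = 18% | 0.06 / √[(0.24 × 0.76 + 0.18 × 0.82) / 2] ≈ 0.15 |

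A false imbalance above the 10% threshold is therefore possible if s differs enough between groups. Nothing in the documents shows that it does.

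**The case against.** The strongest case against concerns weight, since the mismatch between heading and codes is plain on the page.

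- **Code counts are not patient counts.** A patient with at least one of the 25 listed codes during the 365 days is still flagged. Only those with complication codes alone are missed, and that share could be small. No difference by race or metastatic status is shown. This stands, and no patient-level size is claimed.
- **Individual rows need not match NCI rows.** The individual congestive heart failure row does repeat its NCI row, which starts "I09.9, I11.0, I13.0, I13.2, I25.5, I42.0", in full (10 of 10 entries). But the COPD row is narrower than the NCI chronic pulmonary row, and the stroke row differs from the cerebrovascular row. The table shows no copying rule, so how the diabetes row arose is a guess. For the same reason, a patient who counts as diabetic in the Charlson score but not in the flag is not by itself proof of error. This stands too, but the finding needs neither argument.
- **It is one flag of 18 in a descriptive study without prespecified hypotheses.** It touches no eligibility criterion or outcome. That limits the damage, but the flag still belongs to the primary-objective table.

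A deliberate restriction to uncomplicated diabetes would be a legitimate choice, but neither the variable name nor the row heading says so. Annex 1 lists no stand-alone document that could. The page break splits the NCI row and leaves the type II row whole, so layout does not explain the mismatch.

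**Conclusion.** The concern holds and should be fixed before programming. The row used for the diabetes flag is the list for diabetes without chronic complication under a type II heading. It contains 25 of the 50 printed diabetes codes and, if E11 is the type II family, 5 of 10 type II codes plus 20 from other families. If all diabetes is meant, reported prevalence can only be understated, by the share of diabetic patients with chronic-complication codes alone. That share is not in the documents. The 50-code denominator is the appendix's own list and is not claimed to be a complete coding standard. The Charlson score is unaffected because it draws on both NCI rows.

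**What to change.** Decide which condition is meant, and make the Section 9.3 name, the Appendix Table 2 heading and the codes agree.

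- **If all diabetes:** head the row Diabetes and define it as the union of the two NCI diabetes rows (50 codes, E10 to E14, .0 to .9).
- **If type II only:** rename the Section 9.3 variable and list all E11 codes and no others.

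The cost is one appendix row and its code array, plus the variable name in Section 9.3 under the second option. No new data and no design change are needed, and every code for the all-diabetes version is already printed in the appendix. A count of patients with only chronic-complication codes at baseline, overall and by race and metastatic status, would show how much the correction changes.
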